8.2. Quality Control

While it was the original intent of the study to conduct quality control measures on 10% of study measures, COVID safety protocols made this infeasible.

Fidelity measures will be asked by data collectors at each data collection time point to participants, as feasible, with a minimum of 10% of visits assessed:

1. Did you receive a "Greenlight booklet" during your child's visit today?
2. Did you and your doctor discuss any specific pages in the booklet during the visit?
3. Did you and your doctor use the Greenlight booklet to set any goals today?

8.3 Measures related to the COVID-specific aims

First, we will conduct a qualitative evaluation of social needs facing low-income families and the degree to which current social supports are adequate to address those needs. Trained interviewers will conduct 1:1 interviews with the primary parent in English or Spanish. They will follow an interview guide grounded in the social ecological model to explore the social and behavioral impacts of COVID19 (Appendix 1). These interviews will occur three times, during July-September 2020, December 2020-February 2021, and April 2021-June 2021. Participants already enrolled in the parent study will be eligible to participate. Recruitment for the qualitative study will occur during previously scheduled data collection visits (i.e., well-child checks) for the parent study.

Second, we will conduct a birth-cohort analysis by engaging the participants who were recruited prior to the pandemic onset (N=117) and those that will be recruited over the next 9 months (N=783, for total N=900). We will add survey measures that are informed by theory (e.g., newly developed coronavirus impact scale, measures of family resilience, etc.)^{143,144} and the qualitative interviews in Aim 1. All newly proposed measures will be obtained at a COVID baseline and the 24-month follow-up. The Coronavirus impact scale will be collected at all additional timepoints beginning at 2 months.

COVID-19 Related Measures (Newly developed, obtained from NIH repository)	
Coronavirus Impact Scale	Measures COVID-19 impacts including changes to daily routines, family income, access to healthcare, access to social supports, family discord, etc. (12 items).
COVID-19 exposure and family impact survey (CEFIS)	Measures COVID-19 stress across multiple domains including number of affected family members, degree of social isolation, and effects of parenting, financial hardship, access to food/medication, etc. (37 items)
Duke COVID-19 Survey (Stress/Anxiety due to COVID-19)	Measures changes in sleep, anxiety, depressive symptoms. (9 items)
Family Assessment Device	General Functioning Sub-Scale. (12 items) ¹⁴⁶
FRAS Subscale	Measures utilization of social and economic resources (11 items)

COVID-19 Related Self-Efficacy	Measures self-efficacy to respond to the psychological and social challenges of the pandemic. (10 items)
--------------------------------	--

9. PARTICIPANT SAFETY AND ADVERSE EVENTS MONITORING

9.1. Potential Risks and Protection against Risks

Human Subjects Involvement and Characteristics: At each academic medical center (Vanderbilt, U Miami, UNC, NYU, Stanford, and Duke), between 100-200 caregiver-child dyads will be recruited over approximately 12-15 months (total N=900-925). Caregiver-child dyads will be recruited by a trained local Research Assistant in the newborn nursery or at the first well-child visit at the local Pediatric Resident Primary Care Clinic and will be followed until the child's 2 year well child care visit. The pediatric residents at each academic medical center who participate in the Pediatric Resident Primary Care Clinic will also be recruited (up to 110 pediatric residents per year over 4 years at each medical center). In addition, other healthcare providers (nurse practitioners, physician assistants, faculty physicians) will be recruited, as local practice variations may allow for non-resident physicians to occasionally provide care for patients primarily followed in a resident-based clinic.

Full inclusion and exclusion criteria for the recruitment of caregiver-child dyads is outlined in the **Research Section**.

This study will target caregivers and their young children. Targeting children this young is deemed necessary to optimally intervene and improve family lifestyles to prevent childhood obesity. Starting at this young age is imperative to promote healthy behaviors during this critical period in which lifelong diet and physical activity behaviors are formed.

Protection Against Risk: Study personnel will comply with all federal, state, and local laws. Particular attention is drawn to the Food and Drug Administration Regulations for human subject research (45 CFR 46), children as a vulnerable population (45 CFR 46 Subpart D), and the International Conference on Harmonization (ICH) Guidelines for Good Clinical Practices (Guidance for Industry E6).

We will be administering the PHQ-9, which includes a question about self-harm to caregivers as part of the participant survey. If a caregiver reports severe symptoms of depression (PHQ-9 score of 20 or higher) or endorses the 9th item on the PHQ-9, indicating thoughts of self-harm, we will enact the following depression protocol. A notification in the REDCap database will alert the RA/member of the research team administering the survey, who will give the caregiver the resources handout, which includes crisis hotline numbers and mental health services, and follow existing site-specific clinic processes to alert the local clinical team in real time. The site PI (or the clinic social worker, if available) will follow up with the caregiver within 48 hours to discuss and will refer her to the ER or crisis hotline if needed.

IRB approval: Any additional protocol, informed consent documents, and all types of volunteer educational information will be submitted to all the IRB for review and must be approved before the study is initiated. Any amendments to the protocol must also be approved by the IRB prior to implementing any changes in the study. We will also keep the IRB informed of any significant adverse events.

Adverse Events: Although adverse events are not anticipated from the nature of this study, all volunteers will be under the care of experienced providers and the policy of the 6 participating Academic Medical Centers is to provide all necessary care to volunteers who experience an adverse event during a study. The investigator or designate is responsible for the detection and documentation of adverse events (AE) and serious adverse events (SAE) in persons participating in this study. At each clinical evaluation and safety evaluation during the study period, the investigator or site personnel will document any AEs or SAEs, as detailed in this protocol. A telephone number will be provided to caregivers who will be asked to immediately report any adverse events. Adverse events (ER visits, and hospitalizations) and any concerns from participants will formally be assessed monthly by the local site Co-PIs. If a subject concern is reported, the local PI will consult with [name] (Contact PI) to assess severity and determine if the event is related to participation in the study. If the study intervention is implicated in the adverse event the caregiver and their child will be removed from the study and notifications of appropriate authorities will occur.

Safety Monitoring Oversight: The Data Safety and Monitoring Board (DSMB) in conjunction with the Steering Committee at each Academic Medical Center will oversee the safety of volunteers participating in the study as needed. The PI at each site will be responsible for timely identification of adverse events and will report them to the chair of the DSMB and IRB if they occur.

Compliance with Protocol: Each investigator must adhere to the protocol as detailed in this document. Each investigator will be responsible for enrolling only those volunteers who have met study eligibility criteria. A physician may implement a deviation from, or a change in, the protocol to eliminate immediate hazard(s) to trial subjects without prior DSMB and/ or IRB approval. As soon as possible, the implemented deviation or change, the reasons for it and if appropriate, the proposed protocol amendment(s) must be submitted: 1) To the IRB for review and approval/favorable decision, 2) To DSMB for agreement; and if required, and 3) To the regulatory authority(ies). Any protocol violations must be reported to the DSMB in a timely manner. Protocol violations that result in an adverse event must be reported on an AE/SAE form and on the protocol violation form. A written report should be sent to the DSMB as soon as possible. The report should include: 1) Nature of the error, 2) Standard reporting information (patient's clinical status before and after the event), 3) Steps taken to review the error, and 4) Steps taken to assure the error will not occur again. Protocol violations must also be reported to the IRB. Protocol deviations, which are departures from the protocol for which the staff has no control (e.g. subject misses a study visit for a given day), should be documented in the study record and the DSMB is not required to be notified of these protocol deviations.

Confidentiality: The results of the research study may be published, but study participant names or identities will not be revealed without express written consent of the study participant. Records will remain confidential. To maintain confidentiality, the principal investigators will keep records in locked cabinets and results of tests will be coded to prevent association with study participant names. Study participant records will be available to the study staff, and the local participating Academic Medical Center IRB. Data will be collected during this study and stored with code numbers as the only identifiers. Surveys completed by study participants will not contain any identifying information and will also be entered into a comprehensive data collection database (REDCap). REDCap (Research Electronic Data Capture) is a secure, web-based application designed exclusively to support data capture for research studies. All data will be maintained in password access databases behind a secure firewall. In addition, all communication between our iOTA software's application programming interface (API) and third-party software is encrypted using SSL, and information on Greenlight website participant dashboards will not contain identifying information.

9.2. Potential Benefits

Potential benefits to the caregiver and their child for participating in this study include: (1) improved knowledge and health behaviors related to healthy child behaviors (2) reduction in the development of overweight in the child at age 2, and (3) improved use of clinical and preventive services. There is no guarantee of benefit to the volunteer from this study. Participants will also obtain modest financial compensation for their time and receive items that reinforce healthy behaviors ("tangible tools"). As outlined above, the risks to the volunteers of this study are reasonable in light of the potential benefits. Potential benefits to Pediatric Healthcare providers who participate in the study include: (1) improved health communication skills (intervention arm), and (2) improved knowledge and training in promotion of health lifestyles and obesity prevention. As outlined above, the risks to the volunteers of this study are reasonable in light of the potential benefits.

Potential Risks: This is a low-risk study. The main risk would be loss of confidentiality if a study database were compromised.

9.3. Safety Monitoring Plan

The following section outlines the respective action responsibilities of different study parties:

Responsible Person Activities

Local Principal Investigator

1. Evaluate adverse events for severity, causal relationship to study intervention, and action taken and outcome.
2. Promptly report all severe adverse events (SAEs) and unexpected events to DSMB, and IRB.
3. Notify the DSMB and IRB of any new safety information.
4. Provide written response to DSMB and IRB action plans if required.

5. Provide meeting minutes and adverse event reports to DSMB.
6. Respond to any recommendations from the DSMB.
7. Evaluate study components and content for appropriateness, report adverse events associated with these components to the Contact PI.
8. Evaluate screening data for clinically relevant depression, caregiver contact, and appropriate referral to community resources for support and treatment.
9. Notify IRB of recommendations to modify or suspend studies.

Local Research Assistant

10. Complete the IRB Adverse Event Report for each event.
11. Provide local Principal Investigator appropriate documentation for review and recommendations.

DSMB

12. Ensure that the protocol has specified guidelines regarding the identification and procedures for the reporting of adverse events.
13. Review summary reports and tabulations of adverse events.
14. Recommend continuation, modification, suspension of clinical studies based on clinical significance of events.
15. Maintain written records of all communication, assessments and recommendations as well as all materials reviewed.
16. Ensure review process is free from conflicts of interest.

9.4. Informed Consent Documents

Please see Appendix 2 for the current informed consent documents.

10. BLINDING

10.1 Introduction

In all clinical trials, the potential for bias is one of the main concerns. Bias arises from conscious or subconscious factors and can occur from the initial design through study conduct, data management, data analysis and interpretation. A general approach to avoid biases is to keep the participants and the investigators blinded to the identity of the assigned arms until all data points are collected.

Guiding principle #1: All Greenlight Plus personnel that are in a position to change the study protocol or its implementation in study participants should be blinded to information that may allow them to do so, from when the study starts until the study ends, with specific exceptions as delineated in this document.

- This means that all investigators and study staff that have the potential to impact the study's outcome, except as outlined below should be blinded to study data aggregated by study arm.

Guiding principle #2: The study statistician and programmers s/he designates will be unblinded to post-randomization outcome, mediator, moderator and process data for the purposes of generating DSMB reports.

- The study statistician will remain objective when carrying out the activities of conducting the trials – preparing randomization schemes, randomizing individual subjects, processing of the data, cleaning and editing the data, preparation of analyses/reports of outcome, mediator, moderator and blinded process data, and transmitting those data to the DSMB.

10.2 Clarification of Terms

- The “study starts” at a site when the first participant signs informed consent (i.e., resident physician prior to training).
- The “study ends” when the outcomes (primary and secondary) have been collected on all participants at the final data collection timepoint.
- Outcome variables – primary and secondary outcomes as described in the study protocol
- Process variables – e.g. training, recruitment, intervention implementation, fidelity, adherence, retention/attrition

10.3 Blinding of Investigators by Data Type

All data collected will be categorized *a priori* into one of 6 categories:

- i. **Demographic information:** including age, sex, country of origin, and contact information is not blinded, either at the individual level or aggregated by arm.
- ii. **Study arm assignment:** is concealed until the time of randomization. To the extent possible (as described below), staff responsible for collecting outcome data will be blinded to study arm assignment after randomization occurs.
- iii. **Post-randomization outcome, mediator and moderator data:** all personnel are blinded to outcome, mediator and moderator data, aggregated by arm, except for the study statistician and DSMB.
- iv. **Post-randomization, individual level process data:** these variables will be specified *a priori* and noted in the study protocol, or clearly identified in an amendment to the study protocol. They may be viewed Principal Investigators throughout the study and may also be shared with the interventionists, Project Coordinator, Co-investigators, or Managers. Arm-level process data may be viewed by the Principal Investigators and shared with the interventionists, Project Coordinator, Co-investigators or Managers.
- v. **Post-randomization, blinded process data:** investigators and study staff will be blinded to these, aggregated by arm, with the exception of the Statistician, programmers they designate, and the DSMB.
- vi. **Safety data:** are collected for the purpose of insuring participant safety. These will be made available to principal investigators throughout the study. They will be aggregated by study arm.

10.4 Summary of Blinding by Personnel Type

The study arms are, BY DESIGN, not able to be totally blinded. However, some blinding can be maintained. Measurement staff should not be informed of the intervention that individual participants are receiving and should have **no role** in the delivery of the intervention. Efforts should be made to avoid participant (child/parents) interactions that result in open chatting with assessors about the interventions they have

received. Measurement staff should be trained to end any such communication when initiated by participants.

Specifically, we will take steps to blind the study staff (e.g., research assistants) to family study status to the greatest extent possible. For example, we will collect baseline measures before randomization. If feasible, study staff will collect follow-up measures without knowing the study assignment of a family. If feasible we will collect measures related to mobile platform use through electronic surveys that do not require study staff engagement. **HOWEVER**, it may not be feasible to truly blind the study staff to family study status – if: 1) study staff need to help provide technical support for the use of IOTA/Greenlight Platform, and/or 2) study staff need to ask questions face-to-face to families (and possibly residents/clinicians) about their engagement with the technology intervention. Despite these limitations, we will make all reasonable efforts to maintain blinding of outcome assessors, especially those responsible for measuring height and weight data (the primary outcome).

Investigators/staff are blinded as to arm of an individual participant	NOT POSSIBLE
Individual child and/or parent participants are blinded as to the intervention they are receiving	NOT POSSIBLE
Main outcome assessors are blinded as to the intervention the individual participant is receiving	YES (to the extent possible, see above)
Investigators and all study staff, except statisticians/analysts, are blinded as to ALL OMM and blinded process data aggregated by arm	YES
Site staff are unblinded to the aggregated by arm process measures identified a priori or by amendment to the protocol as unblinded	YES

10.5 Unblinded Process Data

There may be specific process data collected in one or more arms that the Principal Investigator and study staff want to review aggregated by arm before the end of the study. Those variables will be declared *a priori*. Those variables will include:

- Number of texts messages sent, received, and expected
- Number of text message responses (to goal setting and follow-up)
- Number of intervention surveys sent and number of responses
- Number of website access and clicks in website
- Attendance at Clinic Visits

Should sites wish to examine additional blinded process variables aggregated by arm, after the study has begun, those requests would be approved by the steering committee and the DSMB, and those variables will be clearly listed as unblinded variables in an amendment to the study protocol.

10.6 Interim Analysis: Not Planned

In Greenlight Plus, there will be no planned interim analysis of the primary outcome and so only the study or independent statisticians/analysts preparing and presenting the analysis to the DSMB, as well as the DSMB, are unblinded.

Interim analyses may be performed on measures/data that are collected after randomization providing they are 1) not the primary outcome or analyses and 2) they do not require adjustment by study status (resulting in unblinding).

10.7 Communication of the Policy for Blinding

To ensure that this policy is clearly understood and communicated, all Greenlight Plus study principal investigators and study staff will affirm the statement below. This can be completed by email to the lead study coordinator. Over the course of the study as new personnel are hired, they will also confirm compliance.

11. STUDY DESIGN, STATISTICAL CONSIDERATION AND ANALYSIS PLAN

11.1 Analysis Plan

We will examine baseline characteristics of the two treatment arms using percentiles for continuous variables and percentages for categorical variables. The primary outcome is child weight for length (WFL) trajectory and secondary outcomes include: WFL Z-score, BMI Z-score, and the percent of children with overweight and/or obesity at 24 months. We will conduct *intent to treat* analyses that compare *the growth trajectories for children in the Greenlight Plus and Greenlight arms over the two years of follow-up*. We choose, as our primary outcome, WFL as opposed to Z-score or percentile because raw values have properties that are superior to standardized outcomes when conducting longitudinal growth modeling,¹⁴⁷ particularly when variables included in standardizations are included in regression models. Recent literature has highlighted problems with BMI-Z score (and other standardized BMI outcomes) for measuring extreme obesity (i.e., BMI percentiles >99%), especially in intervention contexts.¹⁴⁸ While the literature often reports Z-scores, we only include them as a secondary outcome because we believe their limitations outweigh their benefits. We chose WFL as opposed to BMI as our primary outcome since, for children age 0-2, the CDC recommends basing standards on WFL over BMI.

For primary and quantitative secondary outcome analyses, we will test the overall treatment effect (i.e., the combined treatment main effect and the treatment by age minus one month interaction) with a two-sided 0.05 significance level. To account for within-patient and within-site correlation, we will use linear mixed effects models.¹⁴⁹ From these models, we will estimate non-linear intervention effects across the age range (one through 24 months) using restricted cubic splines. Though the study will be randomized, eliminating the potential for confounding, we will control for baseline precision variables believed to be associated with outcomes, including, birth weight, gender, race and ethnicity, caregiver health literacy, caregiver's primary language, annual household income, food insecurity, and years of education. For the analysis of

overweight and/or obesity at 24 months, we will fit a longitudinal logistic regression model and summarize the results at the 24-month age to estimate and test for the intervention effect.

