The original Greenlight Intervention. The initial efficacy trial of the Greenlight intervention was funded by NIH and applied evidence-based health literacy and health communication approaches to support clinician counseling and promote family engagement to prevent childhood obesity in children 2-24 months of age. The study successfully recruited and followed 865 English- and Spanish-speaking families and over 400 pediatric resident physicians in a cluster randomized trial. The study found improvements at 24 months at one site, but not the other, and this lack of improvement at 24 months was thought to be due to: 1) suboptimal engagement between 0-2 months (pre-intervention) and 18-24 months (no well child checks), and 2) lack of family support outside the clinical setting. The proposed study will evaluate the scalability/effectiveness of a more robust Greenlight program that includes additional clinical toolkit support starting at the first newborn visit and leverages technology to provide asynchronous support outside the clinical setting particularly at 18-24 months of life with children's changing feeding patterns. Prior studies across diverse populations have demonstrated the value of digital health platforms to improve patient/family behavior change.⁶⁵⁻⁶⁹

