6.5. Techniques for Retention

We strive to achieve an 80% retention rate with our recruitment and retention strategies outlined above. Our retention plan includes:

- 1) developing positive reciprocal relationships between study staff and participants.
- 2) developing a clear protocol that outlines the collection of contact information, systematic contacts, financial incentives, tangible tools, and a participant tracking database;
- 3) utilizing other methods of staying in contact with participants, such as utilizing the Prompt platform and text messaging through Twilio to re-engage participants from both arms of the study, and taking advantage of social media applications like Facebook.
- 4) accessing participant contact information from the Electronic Health Record if contact is lost.
- 5) obtaining primary outcome data (weight and length) from a participant's new health provider if the participant changes clinics during the study. We will ask permission from the participant to do this during the consent process.

Retention Specialist: As one retention method, all participants will receive a dedicated mobile telephone number to contact the study team. A staff member will be dedicated to monitoring this phone number and tracking all information and question reported by participants. Additionally, the Greenlight Plus team will collect multiple contact numbers and the contact numbers of others who may help us re-establish contact with participants.

Incentives: As a thank you for being in the study, we will give participants a gift card right after we do the survey at the times shown on the chart below.

Time Point for Getting Data	Amount Participants Will Get	About How Long the Survey Will Take
T1 (First Visit)	\$20.00	45-60 minutes
T2 (2-weeks)		5-10 minutes
T3 (1 month)		5-10 minutes
T4 (2-months)		10-15 minutes
T5 (4-months)		5-10 minutes
T6 (6-months)	\$20.00	20-30 minutes
T7 (9-months)		10-15 minutes
T8 (12-months)	\$20.00	20-30 minutes
T9 (15-months)		5-10 minutes
T10 (18-months)	\$20.00	5-10 minutes
T11 (24-months)	\$20.00	45-60 minutes

Participants will also receive \$20 for completing the final study visit, where the primary outcome of 24-month weight and length were collected.

Additional Retention Strategies:

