model parameter estimates we generated child growth in simulated Arms of the study. We calibrated treatment effect sizes by assuming, due to randomization, outcome values between the two treatment arms were equal at study initiation, but children in the Greenlight Plus arm gain weight more slowly than in the Greenlight arm and in such a way that 24-month outcomes differ by a fraction of standard deviation in 24 month WFL. Let SD be the standard deviation in each outcome at month 24 (this is calculated based on original study estimates of the random intercept variance, random slope variance, and measurement error variance) and let ES be the effect size expressed as a fraction of SD. We generated and fit datasets 1000 times, conservatively assuming 30% attrition by the end of the study, to examine the power to detect differences in growth rates that induce a range of values for ES. We observed that we will have ample power for all outcomes if the ES is $\geq 0.2SD$ (the differences in trajectories lead to 0.2 SD differences in 24-month outcomes). The power to detect a treatment effect that is equal to 0.2SD is: 0.91 for WFL, 0.94 for WFL-Z, and 0.92 for BMI-Z. Because analyses of behavioral outcomes will involve binary (logistic), ordinal (proportional odds) and continuous (linear) data regression analyses, we focus on the power to detect treatment effects in the binary data setting due to their relatively low power. We assume 15% missing data for each analysis. We report power as a function of prevalence in the Greenlight arm (pG) and the odds ratios (OR) for the Greenlight Plus arm to the Greenlight arm. We calculate at least 80% power to detect a treatment effect (assuming equal sample size per arm): 1) for $pG=0.05$, $OR>2.20$, 2) for $pG=0.10$, $OR>1.83$, 3) for $pG=0.15$, $OR>1.69$, 4) for $pG=0.20$, $OR>1.61$, 5) for $pG=0.25$, $OR>1.56$, 6) for $pG=0.30$, $OR>1.53$, 7) for $pG=0.35$, $OR>1.51$.

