2. Extended the final data collection window from 850 to 912 days allowing extra time for participants to come in for their well-child checks with COVID delays affecting scheduling (updated in table Table 8.3). Priority will still be given to measurements collected in the original window, but a case-by-case acceptance of measurements collected up to day of life 912 will be considered.

Amendment 9 (10/17/22):

1. An additional incentive was added to support retention at the final timepoint. Text was added to section 6.5 of the protocol. That text reads, “Participants will also receive \$20 for completing the final study visit, where the primary outcome of 24-month weight and length were collected.” As some participants had already completed the study at the time of this amendment, all participants who had already completed the study were offered the additional incentive.
2. To support families who could not attend their child’s 24-month child well-child check, the study team offered to mail the family a scale and tape measure to obtain the final weight/length measures (noted in the study database as self-collected). When possible, families took a photo of the measurement and uploaded via secure link to the REDCap database. A study team member was available via phone or secure teleconference (e.g., ZOOM) to provide support.

Amendment 10 (7/13/23):

1. A typo was corrected in the table detailing the timing of survey items (table 8.3) to indicate the outdoor play survey items were collected at 24-months.
2. Minor edits for clarity were made to the statistical analysis plan. In addition, food insecurity was added as a covariate to the primary model, as there is a planned HTE analysis.
3. Section 11.2.1 was updated to indicate that at the 24 month timepoint, height and length measurements might be obtained by abstracting EHR data from sub-

specialty clinic visits, not only limiting to primary care visits, with the goal of improving retention at the primary timepoint.

Amendment 11 (9/6/23):

1. Corrected typos in the protocol including:
 - a. Added "University" to Johns Hopkins to site list on cover page
 - b. Corrected SASH to BASH in Table 8.3 and Amendment 6 language
 - c. Added "annual household" to income for clarification in Section 11.1
 - d. Corrected Amendment 6 language to include "Principal" in titles

Amendment 12 (1/4/23)

1. Added some minor clarifications in the statistical analysis section, Section 11.1.

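### Should the primary test be moved to the 24-month difference, because a joint test over all ages can be positive when the benefit has gone by age 2?

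*Combined protocol and SAP*

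**What the plan says.** Section 8.1 names weight-for-length (WFL) trajectory from baseline to 24 months as the primary outcome. Hypothesis 1 in Section 2 is about the trajectory over two years. Table 8.3 lists weight and length at every visit under the primary outcome measures. In line with this, Section 11.1 states that "we will test the overall treatment effect (i.e., the combined treatment main effect and the treatment by age minus one month interaction") in a linear mixed model, two-sided at 0.05. It adds: "From these models, we will estimate non-linear intervention effects across the age range (one through 24 months) using restricted cubic splines". Knots are not given.

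Other places give the last visit special weight.
- The power paragraph of Section 11.1 scales the effect so that "24-month outcomes differ by a fraction of standard deviation in 24 month WFL". It describes the 0.2 SD case as one where "the differences in trajectories lead to 0.2 SD differences in 24-month outcomes".
- Section 6.5 describes the final visit as the one "where the primary outcome of 24-month weight and length were collected".
- Amendment 10 in Section 12 widened the sources of measurements "with the goal of improving retention at the primary timepoint".
- Section 3 says of the earlier trial that "this lack of improvement at 24 months was thought to be due to" weak engagement early and late, and little support outside the clinic.
- For overweight or obesity, a secondary outcome, Section 11.1 will fit a longitudinal model and "summarize the results at the 24-month age to estimate and test for the intervention effect".

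**The concern.** A joint test asks whether the arms differ at any age. It has no direction and no preferred age, so a small p-value does not show that the difference lasts. If Greenlight Plus slowed growth in the first year and the arms then converged, the primary test could be significant with nothing left at age 2. Readers could still take the result as proof of Hypothesis 1. The power paragraph expresses its effect at 24 months, and the obesity outcome is tested there, so one could conclude that the primary test is aimed at the wrong quantity. The plan has no rule for a significant joint test with no 24-month difference.

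**Working it through.** **Inputs from the documents.** 900 dyads, 1:1; 30% attrition by the end (Section 11.1, power paragraph); ages 1, 2, 4, 6, 9, 12, 15, 18 and 24 months (Table 8.3); two-sided 0.05; effect 0.2 of the 24-month SD; stated power 0.91 for WFL.

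**Assumptions, because the documents give no values.** Random intercept, slope and error shares, with and without serial correlation (722 settings); 3, 4 or 5 knots in three placements; linear dropout; shape of the transient effect.

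**1. The stated 0.91.** It cannot be rederived without the variance components. An unadjusted comparison at 24 months alone has power Φ(0.2 × √(n/2) − 1.96):
- n = 450 × 0.7 = 315 per arm: 0.2 × √157.5 = 2.51, power 0.71.
- n = 450 per arm, no attrition: 0.2 × √225 = 3.00, power 0.85.

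The stated figure exceeds both, so it draws on the repeated measures. A mixed model gives 0.91 ± 0.02 for many variance splits: 60 in one grid for the slope test, 62 for the 2-df test of main effect plus linear interaction. The figure is attainable, and the paragraph says it concerns differences in growth rates.

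**2. Why the joint test can be positive with no 24-month difference.** Write the arm difference at each age as Bβ, where B holds the treatment main effect and the treatment-by-age terms. The statistic W = β̂′Iβ̂ (I = information for β) has q df: q = 2 if age is linear, q = K with K knots. It splits exactly into W = z₂₄² + R, with R on q − 1 df. For q = 4, z₂₄ = 0 and R = 9.6: p = e^(−4.8) × (1 + 4.8) = 0.00823 × 5.8 = 0.048.

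**3. How often.** Power is P(χ²_q(λ) > critical value). Here λ = δ′MB(B′MB)⁻¹B′Mδ, where M is the summed inverse covariance of the visits over dropout patterns, times 900/4 = 225. The effect δ rises from 0 at one month to a peak at 12 months and returns to 0 at 24.

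| Transient effect | Model tested | Joint test positive |
|---|---|---|
| 0.2 SD peak, 1–24 months | 3–5 knots | 0.83–1.00 (median 0.99) |
| 0.15 SD peak | 3–5 knots | 0.55–1.00 (median 0.87) |
| 0.10 SD peak | 3–5 knots | 0.25–1.00 (median 0.49) |
| 0.2 SD peak, 6–18 months only | 3–5 knots | 0.54–1.00 |
| 0.2 SD peak, 1–24 months | linear, 2 df | 0.17–0.99 |

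The 6–18 month row comes from settings calibrated to about 0.91 power; the others use all settings. A separate grid of 125 settings without serial correlation gave 0.97–1.00 for the 4-knot joint test and 0.37–0.97 for the linear one (first effect in the table). The 24-month contrast from the spline models was positive in 0.05–0.06 throughout.

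**4. Power if the contrast decided instead.** At the planned effect (linear, 0.2 SD at 24 months) with 4 knots and 30% attrition, the contrast has power 0.73–0.84. Setting this against 0.91 is not like for like, because the 4-knot joint test does not have 0.91 either. Where the 2-df linear test has about 0.91, the 4-knot joint test has 0.82–0.86 and the contrast 0.78–0.83, so the two are a few points apart. Over wider grids the contrast is often the more powerful of the two.

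**The case for a change.** The strongest case for a change is that the trial was motivated by an earlier study without lasting benefit at 24 months and went to great lengths to secure that measurement: mailed scales, records from other clinics, and a window extended to day 912. The obesity outcome already shows the technique, and a 24-month contrast needs no new data. A test linear in age would not remove the difficulty: under the same transient effect, that model reports 0.08–0.16 SD at 24 months where the truth is zero.

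Much of this stands as description. A significant joint test says nothing about persistence, and the 24-month difference with its confidence interval must be read beside it. It does not show that the test is wrong. The phrase in Section 6.5 explains an incentive, and the words in Amendment 10 belong to a change log. The power paragraph uses 24 months to scale diverging trajectories and sets no decision rule. Section 3 links rapid weight gain in the first 12 months to later obesity, so a first-year effect is within the trial's own rationale.

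A 24-month test also has costs. Early benefit would no longer count. The decision would rest on the age with the most attrition, the widest window, and some home-measured values. Sections 2, 8.1 and 11.1 would all need rewording, since a trajectory outcome judged at one age would be a new inconsistency.

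**Conclusion.** The behaviour is real, but it is not a type I error or a flaw in the plan. If the spline terms are tested, a broad 0.2 SD effect gone by 24 months would very probably make the primary test positive: about 83–100% under the assumed variances and knots. The figure drops to 54–100% for an effect confined to 6–18 months, and to 17–99% if the tested interaction is linear in age, which the wording of Section 11.1 also allows. In each case the stated null, equal trajectories over two years, is false, and rejecting it is correct.

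Whether to judge such a trial on the whole trajectory or at the last visit is a fair trade-off on which statisticians differ. The plan's choice agrees with its outcome and its hypothesis. The planned curve runs to 24 months and overweight or obesity is tested there, so a faded benefit would be visible to anyone reporting the results. Stating the 24-month difference and its interval beside the curve is ordinary reporting of what the model already provides. No change to the plan is needed.
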